4.12.3 Statistical Analysis of Pharmacokinetic Parameters

* Assessment of Dose Proportionality

Power model is used for assessment of dose proportionality.

- Power model:
 - Power model using linear regression method:

Dose proportionality will be assessed for C_{max} , AUC _{tau}, AUC_{0-inf}, and AUC_{0-t} on Day 1 and Day 7 using the PKAS who received single or multiple doses of TCK-276. PK parameters will be used to perform a LS linear regression analysis, using the formula ln_pkvar=A× ln_dose + B, where 'ln pkvar' represents the natural log transformed C_{max} AUC_{tau}, AUC_{0-inf}, and AUC_{0-t} parameters and 'ln_dose' represents the natural log-transformed dose. An estimate of the slope and intercept of the regression line and corresponding 95% CI will be obtained.

The following SAS code will be used:

ODS OUTPUT parameterestimates=est FitStatistics=fit;

PROC REG DATA = PP ALPHA=0.05 PLOTS=ALL;

BY PARAMCD PARAM;

MODEL LNAVAL=LNDOS/CLB;

RUN;

where:

LNAVAL: natural log-transformed PK parameter

LNDOS: natural log-transformed dose level of <drug>

PARAM: PK parameter

If the 95% confidence interval (CI) range for the slope includes 1 and the lack of fit test is not significant (*p*-value < 0.05), the relationship between dose and the PK parameter will be concluded to be dose proportional for the dose range studied.

If the 95% CI range for the slope does not include 1 or the lack of fit test is significant (*p*-value < 0.05), then additional dose proportionality assessments using above power model with narrower dose range will be performed by sequentially decreasing the number of doses either from higher or lower end of dose range studied as shown in below tabular manner for the respective assessments and combinations. The doses for the assessments must be sequential and include at least 3 doses. All the possible combinations of sequential ascending doses in a certain number of doses will be applied for the assessments. The additional proportionality assessments will be repeated until dose proportionality is found in any dose ranges (minimum 3 doses) and the lack of fit test is not significant.

Round	Combination	Range of Doses	Assessment	
		(in mg)		
1 st	With all four-dose studied	10, 25, 75, 175	If no dose proportionality is shown, perform 2nd Round	
2nd	1^{st} – with 3 doses	10, 25, 75	Stop the assessment at this round	
	2^{nd} – with 3 doses	25, 75, 175	even if none of the combinations shows dose proportionality.	
1			1	

Table 4-2 Dose Proportionality Assessments in 2 round as shown below

Note: If all 4 doses cannot be administered because of protocol defined dose escalation stopping criteria, dose proportionality will be appropriately updated.

4.12.4 Pharmacodynamic Analysis, Concentration, and Parameter TFLs, and Statistical Analysis of Pharmacodynamic Parameters

Not Applicable

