Rb-independent and dependent pathways⁶. Cyclin dependent kinase 4/6 likely contributes to the pathogenesis of RA by mediating the proliferation of synovial fibroblasts and the production of MMP-3. The inhibition of CDK4/6 may serve a useful therapeutic strategy for RA patients, particularly those with an inadequate response to existing DMARDs.

This multiple ascending dose (MAD) study will evaluate the safety, tolerability, and pharmacokinetic (PK) of orally administered TCK-276 in both male and female patients with RA.

The study is being conducted to establish a dose range that is well tolerated by the majority of study patients with RA and to provide exploratory data on the potential for the treatment of RA. The results of the clinical study will inform the design and dose selection of subsequent studies.

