2.2.2 Summary of Findings from Previous Clinical Studies

The first-in-human (FIH) Phase 1 SAD study (Study TCK-276-101) evaluating TCK-276 has completed [REDACTED]; 48 subjects have been orally administered capsules ranging from 5 to 185 mg (geometric mean of $AUC_{0-\infty}$: 39.7 to 2,260 ng·h/mL) once daily (QD). Clinical data from the SAD study of TCK-276 showed no drug-related safety signals (i.e., serious adverse events [SAEs], adverse events [AEs] leading to discontinuation). The plasma exposure levels for TCK-276 linearly increased following escalating TCK-276 administration with the proportion of metabolite (TEI-W00595) to parent remaining similar across dose levels. It was noted that no clinically meaningful differences in PK parameters were observed between fed or fasting states for either TCK-276 or its metabolite.

A detailed description of the chemistry, pharmacology, efficacy, and safety of TCK-276 is provided in the IB.

[figure not shown]

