Parameter **Guideline for Derivation** C_{max}, t_{max}, C_{trough}, Obtained directly from the observed concentration-time data. If multiple t_{max} values are observed the earliest value will be reported. AUC_{0-t} The AUC from zero time (pre-dose) to the time of last quantifiable concentration will be calculated by the linear trapezoidal linear interpolation rule. The AUC_{0-t} is the sum of areas up to the time of the last quantifiable sample: $AUC_{0-t} = \int_0^t C_{last} * dt$ where C_{last} is the last observed quantifiable concentration. AUC_{tau} The AUC over the dosing interval (24 hours) will be determined for multiple dose studies using the trapezoidal rule, as stated above. The area from zero time extrapolated to infinite time will be calculated as follows: AUC_{0-inf} $AUC_{0-inf} = AUC_{0-t} + \frac{C_{\text{last}}}{\lambda_z}$ where Clast is the last observed quantifiable concentration. The percentage of AUC_{0-inf} obtained by extrapolation will be calculated as follows: %AUCex $\% AUC_{ex} = \frac{AUC_{0.inf} - AUC_{0.inf}}{AUC_{0.inf}} \times 100 .$ The apparent terminal phase rate-constant (λz) will be estimated by linear 1. λz and $t^{1/2}$ regression of concentration versus time data presented in a log-linear scale. Data are primarily monotonically decreasing in magnitude and are 2. representative of the actual decline in the log concentration-time curve. Only those data points that are judged to describe the terminal log-linear 3. decline will be used in the regression. 4. A minimum number of three data points in the terminal phase will be used in calculating λz with the line of regression starting at any post-C_{max} data point (C_{max} should not be part of the regression slope). Lambda z (λ_z) and other λ_z -related parameters (i.e. t¹/₂, AUC_{0-inf}, CL/F, MRT_{0-inf}, and V_z/F) will be flagged in listings and excluded accordingly from summary tables and statistical analysis of PK parameters, if the adjusted correlation coefficient (R^2 adjusted) is <0.8, and/or the interval used to determine λz is <1.3 times the half-life and/or %AUC_{ex} is >30%, unless otherwise determined by PK Scientist's best knowledge and judgment or if

Table 4-1 Pharmacokinetic Parameter and Estimation

	instructed by the Sponsor.		
	6. The $t^{1/2}$ will be calculated as follows:		
	$t^{1/2} = \ln 2/\lambda z = 0.693/\lambda z$		
	7. Data points may be dropped from the linear regression if the PK Scientist		

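### SAP 4.12.3 concludes dose proportionality from two non-significant results with no margin or precision limit, and its printed condition and SAS code cannot apply the rule

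*SAP*

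**What the plan says.** Protocol 9.3.3.1 asks only that dose proportionality be assessed with a power model for Cmax and AUCtau of TCK-276 on Days 1 and 7. It sets no criterion. SAP 4.12.3 extends this to four parameters (Cmax, AUCtau, AUC0-inf, AUC0-t) and plans estimation: "An estimate of the slope and intercept of the regression line and corresponding 95% CI will be obtained".

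It then adds a yes/no rule. "If the 95% confidence interval (CI) range for the slope includes 1 and the lack of fit test is not significant", then "the relationship between dose and the PK parameter will be concluded to be dose proportional for the dose range studied". In the parenthesis after this pass condition the SAP prints a p-value below 0.05. The next paragraph attaches the same inequality to a significant lack-of-fit test.

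The code the SAP says will be used has the model statement "MODEL LNAVAL=LNDOS/CLB" and the output request "ODS OUTPUT parameterestimates=est FitStatistics=fit".

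If the four-dose fit fails, Table 4-2 sends the analyst to two three-dose ranges, 10 to 75 mg and 25 to 175 mg. Neither document gives an equivalence margin, a maximum CI width or an inconclusive outcome. Protocol 9.4 and SAP 4.20 both state that no formal sample size calculation was done, so no precision was targeted for the slope.

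**The concern.** Failing to reject slope 1, together with failing to reject linearity on the log-log scale, is treated as proof of proportionality. Data that are merely compatible with slope 1 receive the same label as data that pin the slope close to 1. For any true slope other than 1, the chance of the label rises as the data get noisier or fewer.

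Fewer data are foreseeable for AUC0-inf. Under SAP Table 4-1, parameters that depend on the terminal phase and fail the fit criteria "will be flagged in listings and excluded accordingly from summary tables and statistical analysis of PK parameters", unless the PK scientist or sponsor decides otherwise. The AUC0-inf regression may therefore have fewer than 6 patients per dose.

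Two faults of execution are separate from this. The printed p-value condition contradicts the words it qualifies. The code produces only half of what the rule needs, because the `CLB` option gives confidence limits for the coefficients and nothing requests or saves a lack-of-fit test.

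At stake is a sentence in the study report. Protocol 2.1 says "The results of the clinical study will inform the design and dose selection of subsequent studies", and a stated finding of proportionality is the kind of result that gets carried forward.

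**Working it through.** The documents give no precision or power figure for the slope, so there is none to reproduce.

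**Inputs.** Doses 10, 25, 75 and 175 mg with 6 active patients each (SAP 3.1 and Table 4-2). Two-sided 95% CI (SAP 4.12.3). The between-patient CV is not in the documents: 30, 40 and 50% are assumed, with 20% as a low case. Illustrative true slopes are 1.00, 1.12 and 1.20. The value 1.12 comes from the single-dose study in Protocol 2.2.2, where "48 subjects have been orally administered capsules ranging from 5 to 185 mg" and geometric mean AUC0-inf ran from 39.7 to 2,260 ng·h/mL. If the ends of that range belong to the lowest and highest doses, ln(2260/39.7)/ln(185/5) = 4.042/3.611 = 1.119. It is a two-point figure from single doses of capsules. The value 1.20 is an assumption.

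**Size of the departures.** Dose-normalised exposure changes over 10 to 175 mg by 17.5^(slope − 1): 17.5^0.12 = 1.41 and 17.5^0.20 = 1.77.

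**CI half-width.** The log doses are 2.303, 3.219, 4.317 and 5.165, with mean 3.751. Their squared deviations sum to 4.701, so Sxx = 6 × 4.701 = 28.20 and sqrt(Sxx) = 5.311. With sigma = sqrt(ln(1 + CV²)), the half-width is t(0.975, 22) × sigma / sqrt(Sxx):

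- CV 30%: 2.074 × 0.2936 / 5.311 = 0.115
- CV 40%: 2.074 × 0.3853 / 5.311 = 0.150
- CV 50%: 2.074 × 0.4724 / 5.311 = 0.184

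On the exposure-ratio scale these half-widths are factors of 1.39, 1.54 and 1.70 over the dose range.

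**Same estimate, opposite verdict.** An observed slope of 1.12 has a 95% CI of 1.005 to 1.235 at CV 30%, so it is not proportional. At CV 50% the CI is 0.936 to 1.304, so it is proportional if lack of fit also passes. The second interval allows dose-normalised exposure ratios from 17.5^(−0.064) = 0.83 to 17.5^0.304 = 2.39.

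**Pass rate of the full-range rule.** 200,000 simulated trials per cell, ordinary least squares, slope CI includes 1 and lack-of-fit p >= 0.05:

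| True slope | Patients per dose | CV 20% | CV 30% | CV 40% | CV 50% |
|---|---|---|---|---|---|
| 1.00 | 6 | 90.2% | 90.1% | 90.2% | 90.3% |
| 1.12 | 6 | 12.7% | 43.2% | 61.4% | 71.0% |
| 1.20 | 6 | 0.1% | 6.5% | 23.8% | 40.3% |
| 1.12 | 4 (assumed) | 29.8% | 59.0% | 72.0% | 78.4% |
| 1.20 | 4 (assumed) | 1.7% | 20.5% | 42.5% | 56.8% |

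The 90% in the first row is close to 0.95 × 0.95 = 0.9025, one factor for each condition, and does not depend on CV. With the CI condition alone, which is all the printed code supports, slope 1.12 with 6 per dose passes in 45.4, 64.6 and 74.8% at CV 30, 40 and 50%.

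**Printed p-value condition.** Read literally (CI includes 1 and lack-of-fit p < 0.05), a truly proportional drug passes the full range in about 5% of trials instead of about 90%.

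**Second round.** Adding the two three-dose ranges, at least one range is declared proportional in 89% (CV 30%) and 95% (CV 50%) of trials at slope 1.119, and in 60% and 87% at slope 1.20. The label then covers a narrower range, over which the departure is smaller.

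**Top dose.** The protocol gives 150 mg for Cohort 4 and the SAP 175 mg. With 150 mg the half-widths are 0.120, 0.158 and 0.193 at CV 30, 40 and 50%, so the picture does not change.

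**The case against.** The study is exploratory, Protocol 9.1 states no hypotheses, and PK is a secondary objective. Dose escalation does not use this verdict. The slope, its CI, dose-normalised parameters and the log-log plot are all planned, so a reader can see the imprecision. The exposure ratio is only a transformation of the planned CI. The pass rates rest on an assumed CV, and at 20% the rule rarely passes slope 1.12 or 1.20. The single-dose slope has no uncertainty attached, and Protocol 2.2.2 itself describes exposure as rising linearly. No relevant departure is defined, so a pass at slope 1.12 is not demonstrably an error. A margin rule can be more lenient: a 90% CI within a 2-fold exposure ratio passes slope 1.12 in 69% of trials at CV 30%, against 43% under the SAP rule. The intended p-value condition is clear from the next paragraph.

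Most of this stands, and it limits the weight of the point. It does not rescue the rule. An exploratory study without hypotheses has less need of an automatic verdict, and the protocol did not ask for one. The direction of the fault does not depend on the CV: for any slope other than 1, worse data pass more often. The leniency of a 2-fold margin is a reason to choose any margin with care or to use none. It does not justify inferring proportionality from a CI that merely includes 1. The missing lack-of-fit request is not answered.

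**Conclusion.** The point holds and should be corrected before the analysis is run. As written, the SAP turns two non-rejections into a positive conclusion with no limit on imprecision. At CVs of 30 to 50% it would call a drug proportional over the full range in 43 to 71% of trials when the true slope is 1.12, and in 6 to 40% when it is 1.20. These figures rest on the assumed CVs, 6 evaluable patients per dose, and true slopes chosen for illustration. The p-value inequality in the pass condition is wrong as printed, though its intent is clear. The code cannot apply the rule it accompanies. The harm is confined to a wrongly confident statement in the report, because the estimates behind it will be shown and escalation does not depend on it.

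**What to change.** In SAP 4.12.3:

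- Report the slope with its 95% CI and the implied dose-normalised exposure ratio with its CI: (highest dose / lowest dose in the fit)^(slope − 1), which is 17.5^(slope − 1) over 10 to 175 mg. Do not conclude proportionality because the CI includes 1.
- If a yes/no verdict is kept, require the CI to lie inside an interval that the sponsor pre-specifies and justifies, and report any other result that does not exclude proportionality as inconclusive.
- State the number of patients in each fit, above all for AUC0-inf.
- Correct the pass condition to p >= 0.05.
- Add `LACKFIT` to the MODEL statement and save the output table that holds the test.
- Present three-dose fits as descriptive, each for its own range and beside the full-range result.

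This needs no new data and no protocol change. If the SAP is already final, its Introduction provides a modification form for the purpose. The cost is that some parameters may be reported as inconclusive.

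A margin also has a price. A 90% CI within a 1.5-fold ratio (slope within 1 ± ln 1.5/ln 17.5 = 0.142) passes a true slope of 1.00 in only 60, 21 and 5% of trials at CV 30, 40 and 50%. A 2-fold ratio (1 ± 0.242) passes slope 1.00 in 99, 89 and 68%, and slope 1.12 in 69, 49 and 37%. No margin is recommended here; estimation alone avoids the choice.

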4.13 Safety Evaluation

All safety summaries and analyses will be based upon the SAF as defined in Section 4.4.1.

All summaries will be provided by cohort and treatment.

Placebo across cohorts will be pooled.

4.13.1 Adverse Events

All outputs for AEs/treatment-emergent adverse events (TEAEs) will be based on the SAF unless specified separately in TLF shells. AEs are to be classified by using Medical Dictionary for Regulatory Activities (MedDRA®), Version 25.0 or higher and assigned to a System Organ Class (SOC) and Preferred Term (PT).

All AE will be summarized by MedDRA terms and treatment groups. It will include evaluation of the number of AEs and the number and percentage of patients reporting at least one AEs.

Summaries of AEs will include the following:

- Incidence of AEs Overview (by cohort/treatment and overall)
- Incidence of TEAEs (by cohort/treatment and overall, SOC, and PT)
- Incidence of TEAEs by relationship (by cohort/treatment and overall, SOC, and PT)
- Incidence of TEAEs by maximum severity (mild/moderate/severe, by cohort/treatment and overall, SOC, and PT)
- Incidence of TEAEs leading to discontinuation of study treatment
- Incidence of SAEs
- Incidence of TEAEs Related to IMP by maximum severity (mild/moderate/severe, by cohort/treatment and overall, SOC, and PT)

Summary tables will contain counts of patients, percentages of patients in parentheses, and the number of events where applicable. A patient who has multiple events in the same SOC and PT will be counted only once in the patient counts, but all events will be included.

All Adverse Events (AEs)

Adverse events will be individually listed per patient number, presenting assigned treatment, verbatim term, Primary SOC, PT, treatment emergence (yes or no), date and time of onset, date and time of last study drug administration before AE, time from onset since last study drug administration, severity and seriousness, relationship to study drug, the required action taken, outcome, if it is a reason for drop out, and if it is AESI or not.

Treatment-emergent Adverse Event

A TEAE will be defined as any AE that emerge during treatment (i.e., AE which started after study drug administration or pre-existed that worsened in severity after study drug administration) and those will be analyzed for the purpose of safety analysis.

TEAEs will be summarized by SOC and PT, including the number and percentage of patients experiencing events, separately.

Severity

TEAEs will be summarized by SOC, PT, and severity, including the number and percentage of patients experiencing events. If a patient reports the same TEAE more than once within that SOC and PT, the TEAE with the highest severity will be used in the corresponding severity summaries.

In summaries including severity, the following intensity categories will be summarized: 'Mild', 'Moderate', 'Severe'. Subjects who experience the same event multiple times will be included in the most severe category. Events with missing intensity will be considered as 'Severe' events for summary purposes but recorded as missing in the listings.

If severity is reported by Common Terminology Criteria for Adverse Events (CTCAE) grade, then summary of severity will be presented using CTCAE grade.

Relationship (Causality)

TEAEs will be summarized by SOC, PT, and causality, including the number and percentage of patients experiencing events. Relationship to study drug will be tabulated respectively. If a patient reports the same TEAE more than once within that SOC and PT, the TEAE with the worst-case

relationship to study drug will be in summaries including relationship to study treatment, the following relationships will be summarized: 'Not related', 'Related'. Patients who experience the same event multiple times will be included in the most related category. Events with missing relationship will be considered as 'Related' to the last given study drug for summary purposes but recorded as missing in the listings.

Adverse Events of Special Interest (AESI)

Based on CDK4/6 inhibition mechanism of action, the following AEs will be defined as AESIs:

- Myelosuppression: Hematology including monitoring for neutropenia, leucopoenia, thrombocytopenia, and increased tendency to bleed
- Embryo-fetal toxicity:
- Interstitial lung disease: Pulmonary symptoms (dyspnea, pyrexia, and cough)
- Gastrointestinal toxicity: e.g., diarrhea, nausea, vomiting, and abdominal pain.

Adverse events of special interest (AESI) will be summarized by SOC and PT, including the number and percentage of patients experiencing events. Listing of AESI will be provided.

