8.4 Adverse Events, Serious Adverse Events, and Other Safety Reporting

The means of obtaining AE data should be described (volunteered, checklist, or questioning) as should any specific rating scales used and any specifically planned follow-up procedures for AEs or any planned re-challenge procedures.

Consider whether there any protocol-specific events that may need expedited reporting, or alternatively, are not required to be reported. Provide guidance for Investigators. If there is a specific AE that will be of special interest it should be described in Section [8.4.6](#).

The definitions of AEs and SAEs can be found in [Appendix 3](#) (Section 10.3).

AEs will be reported by the patient (or, when appropriate, by a caregiver, surrogate, or a legally authorized representative [LAR]).

The Investigator and any qualified designees are responsible for detecting, documenting, and reporting events that meet the definition of an AE or SAE and remain responsible for following up AE that are serious, considered related to the study intervention or the study, or that caused the patient to discontinue the study intervention (see Section [7](#)).

The method of recording, evaluating, and assessing causality of AEs and SAEs and the procedures for completing and transmitting SAE reports are provided in [Appendix 3](#) (Section 10.3).

Screening form including AE questioning will include specific questions regarding symptoms of COVID-19: fever, cough, dry throat, difficulty breathing, and potential exposure in the past 2 weeks.

Confirmed and suspected SARS-CoV-2 infection and COVID-19 will be recorded in the AE fields.

8.4.1 Time Period and Frequency for Collecting Adverse Events and Serious Adverse Events Information

All AEs and SAEs will be collected and recorded for each patient from the date for signing of ICF until Day 14 Follow-up Visit or early termination visit i.e., the patient has discontinued or completed Day 14 visit in the SoA ([Table 1-1](#)).

All SAEs will be recorded and reported to the Sponsor or designee within 24 hours of awareness, as indicated in [Appendix 3](#) (Section 10.3). The Investigator will submit any updated SAE data to the Sponsor within 24 hours of it being available.

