9.3.2.3 Adverse Events

All AEs will be listed and coded according to the MedDRA. Adverse events will be individually listed per patient number, presenting assigned treatment, verbatim term, Primary SOC, PT,

treatment emergence (yes or no), date and time of onset, date and time of last study drug administration before AE, duration, time from onset since last study drug administration, frequency, severity and seriousness, relationship to study drug, the required action taken, outcome, if it is a reason for drop out, and if it is AESI or not. The treatment emergent AEs will be summarized by MedDRA terms and treatment groups. It will include evaluation of the number of AEs and the number of patients reporting these AEs.

SAEs will be listed separately.

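### SAP 4.13.1 puts no treatment-emergent limit on the AE overview, SAE and AESI summaries, so read literally they can count pre-dose events under a dose group

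*SAP*

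**What the plan says.** Protocol 9.3.2.3 states: "The treatment emergent AEs will be summarized by MedDRA terms and treatment groups". For serious events it says only "SAEs will be listed separately", and it plans no separate AESI table.

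SAP 4.13.1 has a nearly identical sentence with a different subject: "All AE will be summarized by MedDRA terms and treatment groups". It then names seven summaries. Five are restricted to TEAEs: the main table by SOC and PT, the tables by relationship and by maximum severity, the table of events leading to discontinuation, and the table of related events by maximum severity. Two are not restricted: the AE overview and "Incidence of SAEs". The AESI paragraph later in the section has no restriction either: "Adverse events of special interest (AESI) will be summarized by SOC and PT, including the number and percentage of patients experiencing events".

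The section also defines a TEAE as an event that starts, or worsens in severity, after study drug. It says that these are the events analysed for safety. The AE listing carries a yes/no flag for treatment emergence.

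On collection, Protocol 8.4.1 says: "All AEs and SAEs will be collected and recorded for each patient from the date for signing of ICF until Day 14 Follow-up Visit". The schedules in both documents put screening at Days -28 to -2. SAP 4.21 declares one change, to the exploratory population, and none to the AE analysis.

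**The concern.** AE and AESI incidence is part of the primary endpoint. An event before the first dose cannot be caused by the dose. If it is counted under a dose group, the table shows as that group's experience something that happened before any drug was taken.

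The AESI and SAE summaries matter most. For AEs in general, a TEAE table by SOC and PT stands beside the unrestricted output, so a reader can see the difference. For AESIs and SAEs, the unrestricted table is the only incidence table named. Several AESI terms, such as nausea, diarrhea, abdominal pain, cough and pyrexia, can occur without the drug, and the dose groups are very small.

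**Working it through.** **1. The window.** Protocol 4.1 gives about 42 days of participation: 27 of screening, 11 in-house and 4 to follow-up. The schedule reproduces this:

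- Days -28 to -2: 27 days
- Day -1 and Days 1 to 10: 1 + 10 = 11 days
- Days 11 to 14: 4 days
- Total: 27 + 11 + 4 = 42 days

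The pre-dose part is at most 27 + 1 = 28 days, and Days 1 to 14 are the other 14. The pre-dose share of the collection window is w/(w + 14), where w is the number of days from consent to first dose:

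- w = 28: 28/42 = 66.7%
- w = 14: 14/28 = 50%
- w = 7: 7/21 = 33.3%

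**2. Which outputs can take in pre-dose events.**

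| SAP 4.13.1 output | Limited to TEAEs? | TEAE counterpart named? |
|---|---|---|
| Main SOC/PT table | Yes | – |
| By relationship | Yes | – |
| By maximum severity | Yes | – |
| Leading to discontinuation | Yes | – |
| Related, by maximum severity | Yes | – |
| AE overview | No | Main SOC/PT table, in part |
| SAE incidence | No | None |
| AESI by SOC and PT | No | None |

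SAP 4.13 bases all of these on the safety population, which requires at least one dose. Only pre-dose events of patients who are later dosed can enter. SAP 4.2.7 divides observation time into segments, but its on-treatment segment begins at admission on Day -1, and 4.13.1 ties no AE table to it. It does not settle the question.

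**3. Weight of one patient.** Each cohort plans 6 active and 2 placebo patients. SAP 4.13 pools placebo, giving 4 × 2 = 8. One patient whose only event of the type is pre-dose adds:

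- dose group: 100/6 = 16.7 percentage points
- pooled placebo: 100/8 = 12.5 percentage points

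**4. How often.** The documents give no background rate. As an assumption, let p be a patient's chance of a qualifying event in 14 days without drug, constant over time. The chance that at least one of 6 patients has a pre-dose event is 1 − (1 − p)^(6w/14):

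| p (assumed) | w = 7 | w = 14 | w = 28 |
|---|---|---|---|
| 2% | 5.9% | 11.4% | 21.5% |
| 5% | 14.3% | 26.5% | 46.0% |
| 10% | 27.1% | 46.9% | 71.8% |

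This range is not a forecast. The eligibility exclusions lower the rate among patients who reach dosing. The event also changes the group's incidence only if the patient has no treatment-emergent event counted in the same row.

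**The case against.** A reader might infer that the SAP has dropped the protocol's treatment-emergent summary and put an all-AE summary in its place. It has not. The main SOC/PT table is restricted to TEAEs, as are four others, so the summary required by Protocol 9.3.2.3 is still produced. The all-AE output is an addition.

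It is also fair to say that the consequence is not certain. The sentence making TEAEs the events analysed for safety can be read as governing the unlabelled tables. The rows of the overview are not specified, and the table shells mentioned in SAP 4.13.1 are not among the documents.

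For SAEs and AESIs there is no protocol limit to breach. The protocol only lists SAEs, and its endpoint wording for AEs and AESIs has no treatment-emergent qualifier.

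Eligibility removes some of the events in question. Exclusion 26 covers symptoms consistent with SARS-CoV-2 infection, with fever, dry cough and dyspnea among its examples, within 14 days of Screening or Admission. Exclusion 7 covers low blood counts at either visit.

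Finally, the escalation-stopping rules in Protocol 7.1.2 rest on events judged related to study drug, and the listing would let a reader pick out any pre-dose event among 32 patients.

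All of this stands and limits the point. It does not remove it. The two sentences in SAP 4.13.1 point in different directions, and a programmer following the table titles would not filter the SAE and AESI tables. Gastrointestinal events, and respiratory symptoms early in a long screening period, can still occur in patients who are later dosed.

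**Conclusion.** The point holds in a limited form. The SAP's all-AE sentence disagrees with Protocol 9.3.2.3 and sits uneasily with its own TEAE sentence. On a literal reading, the overview, SAE and AESI summaries can count pre-dose events of later-dosed patients under a dose group. Each patient with only such an event moves the incidence by 16.7 points in a group of 6, or 12.5 points in pooled placebo of 8. That size assumes the planned group sizes and the literal reading. The frequency is unknown.

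A reader might go further and infer that the contrast with placebo is materially diluted. For example, take assumed post-dose AESI incidences of 30% on active and 10% on placebo, with 28 pre-dose days at that placebo rate. The table would then show 1 − 0.7 × 0.9² = 43.3% against 1 − 0.9³ = 27.1%, and the difference would fall from 20 to 16.2 points. The documents do not support this as an estimate. They give neither rate, 28 days is the maximum, and the constant background ignores the exclusions. With so few patients, a chance imbalance in pre-dose events could also widen the contrast instead of narrowing it.

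**What to change.** In SAP 4.13.1:

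- Change the subject of the summary sentence from *All AE* to *TEAEs*.
- Restrict the SAE and AESI incidence tables to treatment-emergent events and say so in their titles.
- Show pre-dose events as a separate row in the AE overview.
- Keep all pre-dose AEs and SAEs in the listings, with the treatment-emergence flag already planned.

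If an all-AE summary is intended, declare it in SAP 4.21 as a difference from the protocol.

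The cost is a few words and a filter on an existing flag, with no new data. If the SAP is already final, SAP 1 provides a Statistical Method Modification Form for recording the change.
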